## Section C: Background Information

Supracondylar fracture of the humerus is a very common traumatic injury in pediatric orthopedic practice, accounting for more than half of all elbow fractures and roughly 33% of all pediatric limb fractures. They are classified into 3 types depending on the degree of displacement. Type 1 fractures have no or minimal displacement and can be managed with splinting and casting. However, surgical manipulation via closed reduction and percutaneous pinning with cast placement is usually required in type 2 supracondylar and lateral condyle fractures. Significant tissue interposition in type 3 supracondylar fractures may require an open operation for fracture reduction. These procedures all require general anesthesia, but postoperative pain can delay discharge, increase anxiety, and decrease satisfaction by the patient and parent. In addition, the treatment of pain with parenteral opioids can be associated with side effects like nausea, vomiting, respiratory depression and dysphoria. In adults, regional anesthesia with brachial plexus nerve block provides excellent analgesia while avoiding the side effects of opioids. However, until recently these nerve blocks were not often placed in pediatric patients because of concerns that improper positioning of the needle would result in low success rates, potential injury and toxicity from local anesthetics. Surgeons are also extremely concerned that analgesia from nerve blocks would hinder early diagnosis of a compartment syndrome at the site of injury, increasing the potential for long term injury. Compartment syndrome has an incidence of 0.1-0.3% based on a recent retrospective analysis with the main factor on presentation being a poorly perfused extremity and absent pulses. There are no case reports confirming that this has occurred in children receiving regional analgesia. The recent development of ultrasound guided nerve blocks has permitted a more precise visualization of the needle position and spread of local anesthetics, thus increasing the success rate with lower doses of local anesthetic and reducing needle trauma. Supraclavicular and infraclavicular ultrasound guided blocks of the brachial plexus are relatively easy to perform and have been shown to decrease the time to first rescue analgesia in a retrospective case review. Over 50 brachial plexus blocks have been performed in this patient population during the last 6 months at the Texas Children's Hospital, with the other patients receiving IV analgesia. However, there are no prospective data to show the benefits of brachial plexus blockade over systemic analgesia in children with supracondylar fractures.

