The time taken to place the block will be recorded from the time the ultrasound probe is first placed on the child until completion of local anesthetic injection. The observer collecting postoperative data will not be present when the block is placed, and a band-aid will be placed over the supraclavicular fossa in all patients to maintain blinding of the observer to the group assignment. During the operation patients can receive intraoperative fentanyl, 1 mcg/kg IV at a time, if the attending anesthesiologist believes it is clinically indicated. At the end of the operation, anesthetic gases will be discontinued while the patient breathes 100% oxygen. The trachea will be extubated when the patient responds to commands, and the child will then be taken to the Post Anesthetic Care Unit (PACU) in keeping with standard practices. A validated pain scale (verbal rating scale where 0 = no pain and 10 = worst possible pain ever) will be used throughout to assess the severity of pain in the postoperative period. In keeping with current practice, patients with pain scores >4 will be treated with morphine 0.05mg/kg IV at 10 minute intervals until the score is below 4. Oral acetaminophen with hydrocodone (Lortab elixir 0.15mg/kg hydrocodone) will be administered to children for pain scores between 2-3. Supplemental oxygen, rescue antiemetic and antipruritic drugs will be administered in keeping with standard practices of TCH and the clinical judgment of the Attending Anesthesiologist. The duration of supplemental oxygen therapy, any medication administered and complications (side effects such as nausea, vomiting, itching, respiratory depression, prolonged awakening) will be recorded on the case report form.

The blinded observer will record pain scores within 15 minutes of arrival in the PACU and at 30 minutes, 1,2,6,12,24, and 48 hours after arrival in the PACU. If the child is sleeping at this time, the scores will be recorded when awake. The observer will also document any additional medication, the dose and the time given.

Prior to discharge home, parents will be educated on use of the 0-10 pain scale and given a diary to keep an accurate record of postoperative pain issues through the study period. The goal is to capture maximum pain scores at rest and with movement. Patient and parental satisfaction with pain management and with the global perioperative experience will also be graded on a numeric scale 0-10 scale.

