Time to readiness for discharge will also be measured from the time the patient enters the PACU to when the patient attains an Aldrete score of 9-10. This is a standardized scale used to assess discharge readiness at TCH and is listed below:

Aldrete Scoring System Activity Can move voluntarily or on command 4 extremities 2 2 extremities 1 0 extremities 0  
 Respiration Can deep-breathe and cough freely 2 Dyspnea, shallow or limited breathing 1 Apneic 0 Circulation  
 Preoperative BP (mmHg) BP  $\pm$  20 mmHg of baseline 2 BP  $\pm$  20-50 mmHg of baseline 1 BP  $\pm$  20 mmHg 0 Consciousness  
 Fully Awake 2 Arousalable on calling 1 Not responding 0 Color Normal 2 Pale, dusky, blotchy 1 Cyanotic 0 Score of 10: ready for discharge

If the patient is discharged before the end of a 48 hour period after surgery, they will be given a diary to complete to list all medications given, and to assess their pain at various time intervals (12,24, 48 hours after surgery), along with their satisfaction with pain control. The patient will be contacted after discharge to obtain the data in the diary. Phone calls will also be placed on POD #1,2, & 3 to the family following to assess measured endpoints (pain, medication usage, satisfaction, resolution of nerve block). We will examine the differences in subjects who did or did not return the diaries regarding group assignments, age, gender, ASA physical status, duration of surgery, intraoperative opioids medications, time of the PACU stay, mean and peak pain scores and recorded opioid consumption in the PACU before discharge.

At the time of their follow up visit to the surgeon, a complete physical examination will be done including a neurological evaluation for any nerve injury.

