## G2. Data Analysis

Provide a description of your plan for data analysis. State the types of comparisons you plan (e.g. comparison of means, comparison of proportions, regressions, analysis of variance). Which is the PRIMARY comparison/analysis? How will the analyses proposed relate to the primary purposes of your study?

The primary endpoint of the study will be the peak or maximum pain score in the postoperative period. The secondary endpoints in the study will include (1) Opioid consumption in morphine equivalents (2) Time to first analgesia request (3) Time to achieving discharge readiness (4) Incidence of side effects such as vomiting, respiratory depression, itching, dysphoria, compartment syndrome (5) Patient and parental satisfaction. In order to keep the statistical analysis robust, we will also examine the differences in subjects who did or did not return the diaries regarding: a. group assignments b. age c. gender d. ASA physical status e. duration of surgery f. intraoperative opioids medications g. time of the PACU stay h. mean and peak pain scores and i. recorded opioid consumption in the PACU before discharge. These are known factors k that affect postoperative pain and failure to show a difference in these factors may suggest that the missing 48 hour data can be considered to be missing at random. We will also examine the PACU pain and opioid consumption data(first 2 hr after surgery) for all cases and separately for cases where the diaries were returned with the 48 hour data. If the conclusions regarding the secondary endpoints of pain in the PACU were not altered and the known factors affecting postoperative pain did not differ between those who did and did not return the diaries, it may suggest the conclusions are still robust. Our current plan will be modified to include not only daily phone calls from researchers, but Epic Mychart as well for protected email communication to better gather data.

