Descriptive statistics will be used for each group. The peak and mean pain scores, age, weight, opioid consumption, time to first analgesia and discharge readiness and satisfaction scores will be compared between the two groups using Students t test if the data is normally distributed, and nonparametric tests if the data are skewed. A Fisher's exact test or a Chi Square test with Yates correction will be used to compare the number of patients in each group with side effects as listed above. P values of <0.05 will be considered to be statistically significant.

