## Section H: Potential Risks/Discomforts

### H1. Potential Risks/Discomforts

Describe and assess any potential risks/discomforts; (physical, psychological, social, legal, or other) and assess the likelihood and seriousness of such risks:

All patients in this study will undergo general anesthesia. Risks of general anesthesia consist of airway issues like sore throat, laryngospasm, pulmonary aspiration and hypoxia. Postoperative nausea and vomiting can also occur in up to 40% of children. Serious side effects of general anesthesia can include heart rhythm disturbances, stroke, brain damage, and even death (1 in 200,000). These risks are present even if the child does not participate in the study as the procedure requires general anesthesia. The risks of IV pain medications are the same whether they are on this study or not and will be explained separately (since those risks are not specific to the study). The dose of opioids used in the study population is not different from our current standard practice. Therefore, the side effect profile should be no higher than any other patient undergoing a similar procedure at our institution even if they do not participate in the study. The risks of ultrasound guided supraclavicular block include accidental vascular puncture, local anesthetic toxicity, pneumothorax, and permanent nerve injury. In adults undergoing ultrasound guided regional anesthesia, this has been reported to occur in 0.1 -0.3%. There are few large scale studies in children, the landmark article by in 2006 quotes a complication rate of 23 instances out of 24000 regional anesthetics performed with an incidence of 0 for peripheral nerve blocks. Therefore we believe the risk related to receiving regional blockade as very unlikely. A prospective randomized study was performed in adults undergoing arthroscopy with regional anesthesia. The rate of postoperative neurologic symptoms was 0.4% [2]. Again following standard practice protocols, this risk is no higher than any other patient receiving a supraclavicular ultrasound guided regional blockade at Texas Children's Hospital.

We are unaware of any risks from ultrasound which is used routinely in pregnant women for assessment of the fetus. There is also a risk of loss of confidentiality of data despite the steps taken to prevent this as listed in section K.

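### The side-effect endpoint names mainly opioid-type harms plus compartment syndrome; the block's own complications are not pre-specified, and the follow-up nerve examination feeds no analysis.

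*Combined protocol and SAP*

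**What the plan says.** Section G2 defines secondary endpoint (4) as "Incidence of side effects such as vomiting, respiratory depression, itching, dysphoria, compartment syndrome". The same section then specifies a Fisher's exact or Yates-corrected chi-square test "to compare the number of patients in each group with side effects as listed above", with significance at P below 0.05.

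Section H1 gives the risks of the block as "accidental vascular puncture, local anesthetic toxicity, pneumothorax, and permanent nerve injury". Section I weighs neuropathy, pneumothorax and other complications against the expected benefit, which is less opioid use and fewer opioid side effects.

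Section F2 has the case report form capture complications, with the examples "side effects such as nausea, vomiting, itching, respiratory depression, prolonged awakening". It also states that at the surgical follow-up visit "a complete physical examination will be done including a neurological evaluation for any nerve injury". No endpoint or analysis in G2 refers to that examination.

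Section C links opioids to "side effects like nausea, vomiting, respiratory depression and dysphoria" and reports surgeons' worry that "analgesia from nerve blocks would hinder early diagnosis of a compartment syndrome".

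**The concern.** Three of the five named events (vomiting, respiratory depression, dysphoria) are ones Section C attributes to opioids. Itching is not in that list; I treat it as opioid-type. These are the events the block is expected to reduce by sparing opioids. Compartment syndrome is the one named item that bears on the surgeons' objection to blocks. The harms that belong to the block itself are not named for comparison, although the protocol's own risk-benefit argument depends on them.

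Nerve injury is the clearest case. The examination is planned for all patients. Section F1 excludes children whose radial, ulnar or median nerve function is already compromised, so a deficit in those nerves at follow-up would be new. Fracture or surgery could also cause one, and the randomised control arm is the fair comparator for that. The data will exist, but the plan does not say how they will be used.

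At stake is the safety statement. If the trial reports fewer side effects with the block, readers will take that as a balanced account of harm, when the pre-specified list covers mainly one side. What else counts would be left to decide after the data are seen.

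**Working it through.** **1. The lists side by side.**

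| Event | Named as a block risk (H1) | Named for recording (F2) | Named for comparison (G2) |
|---|---|---|---|
| Vomiting | no | yes | yes |
| Respiratory depression | no | yes | yes |
| Itching | no | yes | yes |
| Dysphoria | no | no | yes |
| Compartment syndrome | no | no | yes |
| Nausea | no | yes | no |
| Prolonged awakening | no | yes | no |
| Nerve injury | yes | follow-up examination only | no |
| Pneumothorax | yes | no | no |
| Vascular puncture | yes | no | no |
| Local anesthetic toxicity | yes | no | no |

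Of the four block risks in H1, 0 are named in endpoint (4).

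**2. The plan's own figure.** G1 gives no calculation for side effects. Its figure of 34 per group concerns peak pain (difference 2, SD 2.9, 80% power, two-sided 0.05). It reproduces: the t-test calculation gives 33.99. It says nothing about rare harms.

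**3. Inputs for rare harms.**
- Number of blocks: G1 states both 40 per group and 188 in total. At the 1:1 ratio in F2, 188 / 2 = 94. The two do not agree, so both are shown.
- Complication rate: H1 gives 0.1% to 0.3% from adults having ultrasound-guided blocks; Section I gives 0.4% to 3%. H1 also cites a paediatric series with no complications among peripheral nerve blocks. At a true rate of zero every figure below would be zero.

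**4. Expected events, n × p, and chance of at least one, 1 − (1 − p)^n.**

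| Rate p | Expected, n = 40 | At least one, n = 40 | Expected, n = 94 | At least one, n = 94 |
|---|---|---|---|---|
| 0.1% | 0.04 | 3.9% | 0.09 | 9.0% |
| 0.3% | 0.12 | 11.3% | 0.28 | 24.6% |
| 0.4% | 0.16 | 14.8% | 0.38 | 31.4% |
| 3% | 1.2 | 70.4% | 2.82 | 94.3% |

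For example, 1 − 0.97^40 = 0.704.

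**5. Would a significance test help?** Against 0 events in the control arm, a two-sided Fisher test first reaches p < 0.05 at 6 events at either size: p = 0.026 with 40 per arm and 0.029 with 94. Power at a true rate of 3% is about 0.1% (40) or 6.4% (94), and effectively nil at 0.4% or below.

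**6. What zero events would show.** The exact two-sided 95% upper limit is 1 − 0.025^(1/n): 8.8% for 0 of 40 and 3.8% for 0 of 94. Both lie above the 3% in Section I, so even a clean result could not exclude the protocol's own upper estimate.

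**The case against.** A reader might infer that the comparison is tilted toward the block by construction, with a child who has a pneumothorax or nerve deficit counted as free of side effects. The documents do not support that, for four reasons.

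- **The lists are open.** Both the G2 endpoint and the F2 recording list give examples only. A pneumothorax could be recorded and even counted. The supportable statement is that it is not named in advance. The same applies to nausea, prolonged awakening and dysphoria.
- **No composite is defined.** The G2 test can be read as one test per side effect. On that reading, leaving an item out shifts no other comparison. Even for an any-side-effect count, the expected omission is at most 1.2 events in 40 blocks, whereas H1 puts postoperative nausea and vomiting at up to 40% of children, or 0.40 × 40 = 16 of 40.
- **The plan does attend to block harms.** Compartment syndrome is a named endpoint. F2 also schedules telephone calls on days 1 to 3 that ask about resolution of the block, as well as the neurological examination.
- **Safety monitoring is in another document.** H2 refers to a Data and Safety Monitoring Plan attached elsewhere, which may specify block complications.

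It is also fair to say that vascular puncture and local anesthetic toxicity from the block cannot occur in an arm without one, so they offer no randomised contrast.

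All of this limits the claim. It does not remove it. The G2 test refers back to a list that names no block complication, a monitoring plan would not by itself change that comparison, and the neurological findings still have no analysis. Low power is a reason to report intervals and does not justify leaving the events unspecified.

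**Conclusion.** The point stands as a gap in pre-specification. The named side-effect comparison covers mainly harms the block should reduce, plus compartment syndrome; the complications the protocol attributes to the block are not named, and the nerve examination is not linked to any analysis. No bias of any particular size is shown, and the primary comparison of peak pain is unaffected.

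Over the stated non-zero rates, the chance that the trial sees at least one block complication runs from 4% to 70% with 40 blocks and from 9% to 94% with 94. The width comes mostly from the documents giving rates that differ 30-fold (3% / 0.1%). These figures assume independent patients, one overall complication rate and every child in the block arm receiving the block. The Fisher results also assume no events in the control arm, which is an assumption for nerve deficit because the documents give no background rate.

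**What to change.** Amend endpoint (4) and its analysis in G2, and the complication list in F2:

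- **Nerve injury:** add new neurological deficit at surgical follow-up, defined against the preoperative examination, as a comparison between the randomised arms.
- **Other block complications:** report pneumothorax, vascular puncture and local anesthetic toxicity as counts with exact 95% intervals in the block arm.
- **Alignment:** make the recorded and compared lists the same, settling nausea, prolonged awakening and dysphoria.
- **Presentation:** report opioid-type and block-type harms as separate groups. For rare events, including compartment syndrome, give counts and exact intervals in place of a p value, and state that a non-significant difference is not evidence of safety.

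The cost is wording in the analysis plan and a few lines on the case report form. It needs no new visit and no larger sample, since the neurological examination is already planned. The drawback is a safety statement that is openly imprecise and may be less favourable to the block.

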## Section H: Potential Risks/Discomforts

### H1. Potential Risks/Discomforts

Describe and assess any potential risks/discomforts; (physical, psychological, social, legal, or other) and assess the likelihood and seriousness of such risks:

All patients in this study will undergo general anesthesia. Risks of general anesthesia consist of airway issues like sore throat, laryngospasm, pulmonary aspiration and hypoxia. Postoperative nausea and vomiting can also occur in up to 40% of children. Serious side effects of general anesthesia can include heart rhythm disturbances, stroke, brain damage, and even death (1 in 200,000). These risks are present even if the child does not participate in the study as the procedure requires general anesthesia. The risks of IV pain medications are the same whether they are on this study or not and will be explained separately (since those risks are not specific to the study). The dose of opioids used in the study population is not different from our current standard practice. Therefore, the side effect profile should be no higher than any other patient undergoing a similar procedure at our institution even if they do not participate in the study. The risks of ultrasound guided supraclavicular block include accidental vascular puncture, local anesthetic toxicity, pneumothorax, and permanent nerve injury. In adults undergoing ultrasound guided regional anesthesia, this has been reported to occur in 0.1 -0.3%. There are few large scale studies in children, the landmark article by in 2006 quotes a complication rate of 23 instances out of 24000 regional anesthetics performed with an incidence of 0 for peripheral nerve blocks. Therefore we believe the risk related to receiving regional blockade as very unlikely. A prospective randomized study was performed in adults undergoing arthroscopy with regional anesthesia. The rate of postoperative neurologic symptoms was 0.4% [2]. Again following standard practice protocols, this risk is no higher than any other patient receiving a supraclavicular ultrasound guided regional blockade at Texas Children's Hospital.

We are unaware of any risks from ultrasound which is used routinely in pregnant women for assessment of the fetus. There is also a risk of loss of confidentiality of data despite the steps taken to prevent this as listed in section K.

### H2. Data and safety monitoring plan

Do the study activities impart greater than minimal risk to subjects?

Yes

NOTE: The answer to the questions in H2 requires the completion of the form: 'Section H – Data and Safety Monitoring Plan' as an attachment in Section S.

### H3. Coordination of information among sites for multi-site research

Is the BCM Principal Investigator acting as the SPONSOR-INVESTIGATOR for this multi-site research?

No or Not Applicable

Is BCM the COORDINATING CENTER for this multi-site research?

No or Not Applicable

## Section I: Potential Benefits

Describe potential benefit(s) to be gained by the individual subject as a result of participating in the planned work.

Patients in the nerve block group may benefit from participating in the study as they may need less additional pain medication after surgery and have fewer side effects from these drugs. If a patient is assigned to the IV group, there are no benefits besides those benefits the patient would experience regardless of participation in the study.

Describe potential benefit(s) to society of the planned work.

Data from this study can be used to determine if children with supracondylar fractures will benefit from regional anesthesia in addition to general anesthesia.

Do anticipated benefits outweigh potential risks? Discuss the risk-to-benefit ratio.

There are no additional risks or benefits in the IV group as this is standard of care. The possible benefits from regional blockade include less pain with less overall opioid usage and less side effects from these drugs. The additional risks of neuropathy, pneumothorax, or other complications are low, and estimated at 0.4%-3% (PBID- 17377115; 19282715). Brachial plexus regional anesthesia is commonly performed at our institution for children having upper extremity surgery. The benefits to society include greater knowledge of the benefits of regional anesthesia in this situation and increased use of this modality in future.

